2.2 DISPOSITION OF PATIENTS

This section describes patient disposition for both patient study status and the patient analysis populations.

Screened patients are defined as any patients who have signed the informed consent.

Randomized patients consist of all patients with a signed informed consent form who have had a treatment kit number allocated and recorded in the IRT database, regardless of whether the treatment kit was used or not.

For patient study status, the total number of patients in each of the following categories will be presented in the clinical study report using a flowchart diagram or summary table:

- Screened patients
- Run-in patients: patient who had a run-in record in IRT
- Screen failure patients (including failures during run-in) and reasons for screen failure
- Nonrandomized but treated patients
- Randomized patients
- Randomized but not treated patients
- Randomized and treated patients
- Patients who completed the 26-week double-blind core treatment period (see [Section 2.5.4](#) as scheduled).
- Patients who did not complete the 26-week double-blind core treatment period (see [Section 2.5.4](#)) as scheduled and the reasons for permanent treatment discontinuation
- Patients who completed the 52-week entire treatment period as scheduled
- Patients who did not complete the 52-week entire treatment period as scheduled , and the reasons for permanent treatment discontinuation
- Patients who completed the study as scheduled.
- Patients who did not complete the study as per protocol and the reasons for study discontinuation
- Patients' end of study status at Week 26 (ongoing, discontinued) and corresponding end of 26-week core treatment status (ongoing, discontinued)

- Patients' end of study status (completed, not completed) and corresponding end of entire treatment status (completed, not completed)
- Status at last study contact

For screened, run in, screen failure, and nonrandomized but treated patients, percentages will be calculated using the number of screened patients as the denominator. All other categories of patients will be presented by treatment group and the percentages will be calculated using the number of randomized patients within each treatment group as the denominator. Reasons for treatment discontinuation will be supplied in tables giving numbers and percentages by treatment group. Patients prematurely discontinued from treatment and/or study, along with reasons for discontinuation, will also be listed.

A summary of the distribution of patients by country and center will also be provided (overall number of patients screened, run-in, randomized, and treated, as well as number of patients randomized, discontinued from study treatment, and discontinued from study for each treatment group).

Patients treated but not randomized, patients randomized but not treated and patients randomized but not treated as randomized will be identified and described in separate listings. The patients of the third category (randomized but not treated as randomized) will be part of efficacy and safety analyses ([Section 2.3](#)). Patients randomized but not treated will be included in efficacy analysis. Safety data of patients treated but not randomized will be reported separately.

The randomization strata [HbA1c at Screening ($\leq 8.5\%$, $> 8.5\%$) and mean SBP at Screening (< 130 , ≥ 130 mmHg)] assigned by IRT will be summarized. The percentages will be calculated using the number of randomized patients as the denominator. The discrepancy between the strata assigned by IRT and the information reported on e-CRF will be listed for all randomized patients.

Kaplan-Meier (KM) plots of the cumulative incidence of double-blind IMP discontinuation due to any reason and due to AE will be provided for the entire 52-week entire treatment period only (see [Section 2.5.4](#)). A listing of these patients, along with the reason for discontinuation treatment, study completion status and the reason for discontinuation study, will be provided.

All important deviations including randomization and drug-dispensing irregularities will be summarized in tables giving numbers and percentages of deviations by randomized treatment group.

Additionally, the analysis populations for safety, efficacy, and pharmacokinetics defined in [Section 2.3.3](#) will be summarized in a table by number of patients in the randomized population.

- Efficacy population: intent-to-treat (ITT) population
- Safety population
- Pharmacokinetics population

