2.1.4 Safety endpoints

The safety analysis will be based on the reported adverse events, hypoglycemia, acute renal failure and other safety information, such as clinical laboratory data, vital signs, electrocardiogram (ECG), physical examination and marker of intestinal transit and absorption, markers of bone and calcium metabolism, etc.

Observation period

The observation period will be divided into 4 epochs:

- The **screening** epoch is defined as the time from the signed informed consent date up to the first administration of the double-blind IMP.
- The **treatment** epoch is defined as the time from the first administration of double-blind IMP to the last administration of double-blind IMP. This epoch includes the 26-week double-blind core treatment period and the 26-week double-blind extension treatment period. The 26-week core treatment period is the time from the first administration of double-blind IMP to the last administration of double-blind IMP on or before Visit 11 (Week 26) [or Day 182 if Visit 11 (Week 26) date is missing].
- The **residual treatment** epoch is defined as the time from the last administration of the IMP to the last administration of the IMP + 15 days (1 day for hypoglycemia).

The treatment-emergent adverse event (TEAE) period will include both **treatment** and **residual treatment** epochs (See the TEAE period for the 26-week core treatment period in [Section 2.5.4](#)).

- The **posttreatment** epoch is defined as the period of time starting the day after the end of the treatment-emergent adverse event period up to the last protocol-planned visit or the resolution/stabilization of all serious adverse events (SAE), adverse events of special interest (AESI) and events of special interest (EOSI), whichever is later.

The on-study observation period is defined as the time from start of double-blind treatment until the end of the study (defined as the last scheduled visit for those who completed the study and the date collected on e-CRF page “Completion of End of Study/Follow-up” for those who did not complete the study).

The post-study observation period is defined as the time from the day after the end of the study until the resolution/stabilization of all SAE, AESI and EOSI if applicable.

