2.4.4.3 Analyses of other efficacy endpoints

The analysis of other endpoints (see [Section 2.1.3](#)) will be descriptive with no formal testing. Summary statistics at scheduled visits based on observed value will be provided by each treatment group. Graphical presentations will also be used to illustrate trends over time as appropriate.

The number (%) of patients who used rescue therapy will be provided by treatment group during the 26-week core (see [Section 2.5.4](#)) and the 52-week entire double-blind treatment periods. A KM curve for the time to first rescue therapy will be presented during the 26-week core treatment period and 52-week entire treatment period (see [Section 2.5.4](#)). The list of patients who used rescue therapy will also be provided.

ESRD is defined as: (1) dialysis that persists for a duration of \geq 90 days, or positively adjudicated as ESRD if dialysis $<$ 90 days; (2) eGFR $<$ 15 ml/min/1.73 m² sustained for at least 30 days or positively adjudicated as chronic; or (3) renal transplant. The number (%) of patients with progression to ESRD at Week 4 or any time later during the study will be summarized. The same analysis will be provided during the period from the first administration of double-blind IMP (or the date of randomization if not exposed) to Week 4 (exclusive). A KM plot will be provided for time to first occurrence of ESRD up to Week 26 and the end of study respectively (see [Section 2.5.4](#)).

The number (%) of patients with >50% decline in eGFR from baseline at each scheduled visit (including Week 26 and Week 52) will be presented. The same analysis will be presented from Week 4 at each scheduled visit afterwards (including Week 26 and Week 52). A KM plot will be provided for time to first occurrence of >50% decline in eGFR from baseline up to Week 26 and the end of study respectively (see [Section 2.5.4](#)).

The number (%) of patients with UACR progression from baseline to Week 26 and Week 52, (ie, from normal to microalbuminuria or from microalbuminuria to macroalbuminuria) will be provided by treatment group respectively. A KM plot will be provided for time to UACR progression up to Week 26 and the end of study respectively (see [Section 2.5.4](#)). Similarly, the number (%) of patients with UACR improvement from baseline to Week 26 and Week 52 (from microalbuminuria to normal or from macroalbuminuria to microalbuminuria) will be provided, as well as the KM plot if appropriate.

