The 26-week core study period is the time from first administration of double-blind IMP to Visit 11 (Week 26) (or Day 182 if Visit 11 (Week 26) date is missing) or the end of TEAE period for the 26-week double-blind core treatment period (as defined above) whichever is later. This is for defining EOS status at Week 26.

Time to event analysis

For time to event analysis/KM plot, time to event (eg, treatment discontinuation, rescue therapy, hypoglycemia, ESRD, etc) is defined as the number of days from the date of the first administration of double-blind IMP (or the date of randomization if not exposed) to the start date of the first occurrence of the event during the respective analysis period.

Patients who did not experience any event during the respective analysis period are considered censored observations. The censoring rules are defined below.

Time to event	Censoring date at Week 26 (1st step analysis)	Censoring date at EOT/EOS (2nd step analysis)
Treatment discontinuation due to any reason	Not applicable	EOT
Treatment discontinuation due to AE	Not applicable	EOT
Time to rescue	min (EOT, Date of W26 visit)	EOT
Time to severe or documented hypoglycemia	See Section 3	Min (EOT+1, EOS)
Time to ESRD	min (EOS, Date of W26/re-allocated W26 eGFR value)	EOS
Time to eGFR decrease	min (EOS, Date of W26/re-allocated W26 eGFR value)	EOS
Time to UACR progression/improvement	min (EOS, Date of W26/re-allocated W26 UACR value)	EOS

Note: (1) Day 182 will be used if Date of Week 26 visit (or date of W26/re-allocated W26) is not available.
(2) Date of EOS will be used if date of EOT is not available; Last contact date will be used if date of EOS is not available.

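### The Kaplan-Meier curve for IMP discontinuation due to AE is labelled a cumulative incidence, but it censors other discontinuations and so sits at or above that quantity

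*SAP*

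**What the plan says.** SAP section 2.2 plans two disposition curves for the 52-week treatment period and names both the estimator and the quantity: "Kaplan-Meier (KM) plots of the cumulative incidence of double-blind IMP discontinuation due to any reason and due to AE will be provided". The same section tabulates reasons for treatment discontinuation as numbers and percentages of randomized patients by arm, and lists the patients who stopped.

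The censoring rules are in SAP section 2.5.4, under time to event analysis. The general rule is that "Patients who did not experience any event during the respective analysis period are considered censored observations". In the table that follows, the row "Treatment discontinuation due to AE" has EOT as its censoring date, and the Week 26 column does not apply. Neither section defines a competing event or specifies a competing-risk estimator.

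Protocol section 10.3.2 defines permanent discontinuation as a definitive decision not to give the patient IMP again. The protocol foresees permanent stops that need not be AEs: patient or sponsor request (10.3.3), continued poor compliance (8.7.1), and code breaking by the investigator (8.3.2).

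**The concern.** Kaplan-Meier treats a censored patient as still at risk of the event and represented by those who remain. That is reasonable for a patient whose follow-up simply ends. It does not fit a patient who has already stopped IMP for good for another reason, because that patient can no longer stop for an AE. Censoring such stops makes 1-KM estimate the risk in a hypothetical setting where nobody stops for any other reason, and only if the two kinds of stop are independent. The SAP names a different quantity, the cumulative incidence of stopping for an AE.

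Two consequences follow. The study report may show two percentages for the same event, one from the plot and one from the table, with the gap produced by the estimator. And an arm with more non-AE stops has its AE curve raised more, which can suggest a tolerability difference that is not there.

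**Working it through.** The plan gives no discontinuation rate and no expected value for this curve, so it has no figure to reproduce. The only input taken from the documents is the planned arm size of 92 (SAP section 1.3). All event rates below are assumptions.

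**Direction.** Just before each AE stop, let S be the proportion of patients with no stop of any kind and S1 the Kaplan-Meier survival that counts AE stops only. The Aalen-Johansen estimate adds S/(number at risk) at that AE stop; 1-KM adds S1/(number at risk). Since S1 is never below S, 1-KM is never below Aalen-Johansen. It is strictly above once a non-AE stop precedes an AE stop.

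**Size.** Let a be the true 52-week cumulative incidence of AE stops and b that of other stops, with constant hazards.

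- Total cumulative hazard: H = -ln(1 - a - b)
- AE-specific part: h = H × a/(a + b)
- Plotted value: 1-KM = 1 - exp(-h) = 1 - (1 - a - b)^(a/(a+b))

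With a = 10%:

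| Other stops b | 1-KM | Value | Excess (points) |
|---|---|---|---|
| 5% | 1 - 0.85^(2/3) | 10.27% | 0.27 |
| 10% | 1 - 0.80^(1/2) | 10.56% | 0.56 |
| 15% | 1 - 0.75^(2/5) | 10.87% | 0.87 |
| 20% | 1 - 0.70^(1/3) | 11.21% | 1.21 |
| 30% | 1 - 0.60^(1/4) | 11.99% | 1.99 |

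Over a wider grid (a from 5% to 20%, b from 5% to 30%) the excess runs from 0.1 to 4.2 points, about 3% to 21% in relative terms. One patient in 92 is 1/92 = 1.1 points.

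**Between arms.** Two arms with the same 10% AE incidence, one with 10% other stops and one with 20%, would plot at 10.56% and 11.21%. The apparent difference of about 0.65 points comes from the estimator alone.

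**Sensitivity to timing.** With a = 10% and b = 15%, if every other stop comes before the AE stops, the curve ends at 0.10/(1 - 0.15) = 11.8%. If every other stop comes after them, it ends at 10% and there is no excess.

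**Finite-sample check.** In 4000 simulated arms of 92 patients per scenario, 1-KM was never below the Aalen-Johansen estimate beyond rounding. The mean excess was 0.87 points (a = 10%, b = 15%), 1.22 (10%, 20%) and 1.87 (15%, 20%), in line with the formula.

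**The case against.** The best reply is that the correct number is already reported. SAP section 2.2 tabulates stops by reason, and section 2.4.5.2 tabulates TEAEs leading to discontinuation. SAP section 1.6 puts everything into a single end-of-study report, when each patient has completed, stopped for an AE or stopped for another reason. The tabulated percentage is then essentially the Aalen-Johansen value at Week 52. This stands, and it limits the harm to one supporting plot. It does not make the plot correct: the SAP names cumulative incidence and specifies an estimator of something else.

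A second reply is that the size rests on chosen rates. That also stands. Only the direction follows from the plan's own text.

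A reader might go further and infer that the plots for ESRD and for eGFR decline above 50% are also wrong, with deaths censored and incidences too high. The documents do not support stating it that strongly:

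- SAP section 2.4.4.3 does not call these curves cumulative incidence. For ESRD it says "A KM plot will be provided for time to first occurrence of ESRD up to Week 26 and the end of study respectively", and the eGFR plot is described in the same way.
- The censoring table, including the row "Time to eGFR decrease", gives EOS for the end-of-study curves and does not mention death. That deaths are censored is an inference from the general rule and from an ESRD definition (dialysis, sustained low eGFR or transplant) without death as a component.
- Assuming ESRD of 10% and deaths of 3%, 1-KM is 10.16%, an excess of 0.16 points. With event rates of 5% to 30% and deaths of 1% to 10%, the excess is 0.03 to 1.8 points and mostly below 1. Protocol section 4.4 itself expects few clinical outcomes.
- A mismatch between plot and table would not show an error here. The main ESRD table counts from Week 4 and the curve from first dose; the eGFR table is by visit and the curve is first occurrence.

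**Conclusion.** The point holds for one curve. As written, the plot of discontinuation due to AE does not estimate the cumulative incidence it is said to show; it sits at or above it. Assuming 10% AE stops, 5% to 30% other stops and constant hazards, it would end at about 10.3% to 12.0%, an excess of 0.3 to 2.0 points. The excess would be zero if all other stops came after the AE stops. Arms with unequal non-AE stops would be raised unequally.

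The any-reason curve is unaffected, since every stop is an event there. For the renal curves, a competing-risk estimator is an optional refinement with a likely effect under 1 point. The plot is descriptive and feeds no test, treatment-effect estimate or step in the testing hierarchy, so this is a minor correction.

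**What to change.** In SAP section 2.2, replace the Kaplan-Meier plot of discontinuation due to AE with the Aalen-Johansen cumulative incidence function by arm. Take discontinuation for any other reason as the competing event, including death on treatment not already counted as an AE stop. In the table in section 2.5.4, say for this row that such patients have a competing event at EOT, and that only patients who complete treatment, or whose follow-up ends without a stop, are censored. Keep Kaplan-Meier for discontinuation for any reason.

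If the plot is left as it is, the least that is needed is to drop the cumulative incidence label for the AE curve and add a footnote that discontinuations for other reasons are censored.

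The same estimator could be used for ESRD and for eGFR decline above 50%, with death as the competing event. For eGFR decline, the SAP would then also need to say how dialysis and transplant are handled.

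The cost is a change to the plotting program and a few lines of SAP text. Reasons and dates of discontinuation, and deaths, are already collected.

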2.2.1 Randomization and drug dispensing irregularities

Randomization and drug-dispensing irregularities occur whenever:

1. A randomization is not in accordance with the protocol-defined randomization method, such as a) an ineligible patient is randomized, b) a patient is randomized based on an incorrect stratum, c) a patient is randomized twice, or d) in a dynamic randomization scheme the treatment assignment is, in fact, not random, due to a computer program error.

OR

2. A patient is dispensed an IMP kit not allocated by the protocol-defined randomization, such as a) a patient at any time in the study is dispensed a different treatment kit than as randomized (which may or may not contain the correct-as-randomized IMP), or b) a nonrandomized patient is treated with IMP reserved for randomized patients.

Randomization and drug-dispensing irregularities will be monitored throughout the study and reviewed on an ongoing basis.

All randomization and drug-dispensing irregularities will be documented in the clinical study report. If the number of irregularities is large enough to make a tabular summary useful, the irregularities will be categorized and summarized among randomized patients (number and percentages). Nonrandomized, treated patients will be described separately. Listings with additional, relevant details will be provided in appendices.

Randomization and drug-dispensing irregularities to be prospectively identified include but are not limited to:

Randomization and drug allocation irregularities
Kit dispensation without IRT transaction
Erroneous kit dispensation
Kit not available
Randomization by error
Patient randomized twice
Stratification error
Patient switched to another site

2.3 ANALYSIS POPULATIONS

Patients treated without being randomized will not be considered randomized and will not be included in any efficacy population.

The randomized population includes any patient who has been allocated to a randomized treatment regardless of whether the treatment kit was used.

For any patient randomized more than once, only the data associated with the first randomization will be used in any analysis population. The safety experience associated with any later randomization will be assessed separately.

The safety experience of patients treated and not randomized will be reported separately, and these patients will not be in the safety population.

2.3.1 Efficacy population

Efficacy analyses will be based on the treatment group allocated by the IRT according to the randomization schedule at randomization visit (as randomized), irrespective of the treatment actually received.

2.3.1.1 Intent-to-treat population

Efficacy analyses will be based on the ITT population, defined as all randomized patients, irrespective of compliance with the study protocol and procedures. Patients will be analyzed for efficacy according to the treatment group to which they are randomized.

2.3.2 Safety population

Safety analyses will be based on the safety population, defined as all randomized patients who receive at least one dose of double-blind IMP (regardless of the amount of treatment administered), analyzed according to the treatment actually received.

In addition:

- Nonrandomized but treated patients will not be part of the safety population; however, their safety data will be presented separately
- Randomized patients for whom it is unclear whether they took the IMP will be included in the safety population as randomized
- When a patient is exposed to both sotagliflozin and placebo, the patient will be analyzed in the appropriate sotagliflozin group (depending on the treatment kits taken [400 mg or 200 mg])
- When a patient is exposed to both sotagliflozin 400 mg (treatment kits) and 200 mg (treatment kits), the patient will be analyzed in the sotagliflozin 200 mg group
- Randomized patients will be excluded from the safety population only if there is documented evidence (ie, all study dates recorded as no medication taken) that patients have not taken the study treatment. If a patient is dispensed double-blind IMP and is lost to follow-up without any documented evidence, the patient will be considered exposed.

